10.2 Placebo (Supplied)

Investigators ordering and/or dispensing supplied agents at any time for study treatment must be currently registered with PMB, DCTD, NCI. A registered investigator must co-sign for other non-registered personnel prescribing the supplied agents

A matching placebo will be provided. It will be identical in appearance to the varenicline.

11.0 MEASUREMENT OF EFFECT

All of the following measures relate to the secondary endpoints.

The primary endpoint of surgical complication incidence rates at 24 weeks after surgery will be measured as described in Appendix X.

11.1 Patient reported measures

For the purposes of this study, patients should be reevaluated every 6 weeks. In total, the time for the patient to complete these forms is approximately 16 minutes at Baseline, 10 minutes at Week 6, 10 minutes at Week 12, and 13 minutes at Week 24.

11.1.1 Tobacco Use Assessment (Appendix IX): We will record the patient’s self-reported smoking status including current use, use during the past 7 days, use since time of last self-report, and use since Target Quit Date (TQD) as appropriate. This form will collect vitals, smoking status, contact made with the tobacco quitline. This will take approximately 3 minutes to complete.

11.1.2 Contemplation Ladder (Appendix III)[77]: The Contemplation Ladder is a visual analog comprised of 11 rungs and 5 anchor statements (item 0, 2, 5, 8, 10), representing stages of change. The response options (0) to (3) correspond with *pre-contemplation*, (4) to (6) represent *contemplation*, (7) and (8) refer to *preparation*, (9) and (10) represent *action and maintenance*, respectively. It is a brief measure of motivation or readiness to change, where (0) is the least motivated and (10) is the most motivated. This measure will be used to screen out those who are not motivated to change (scoring a 5 or below) and therefore lower likelihood of responding to the intervention and completing the study. Two recent studies

of smokers with co-morbid conditions showed the average hospitalized smoker enrolled scored a 6 and above and they found that 70-80% of the enrolled subjects scored an “8” or above.[78, 79] This will take approximately 1 minute to complete.

11.1.3 Smoking Self-Efficacy Questionnaire (SEQ-12; Appendix IV)[80]: Two six-item subscales measuring confidence of smokers in their ability to remain tobacco abstinent in the face of internal stimuli (e.g., feeling depressed) and external stimuli (e.g., in company of smokers). This will take approximately 5 minutes to complete.

11.1.4 Fagerström Test for Nicotine Dependence (FTND; Appendix V)[81]: Predicts smoking abstinence and is correlated with biochemical measures of tobacco dependence. This will take approximately 3 minutes to complete.

11.1.5 Patient Health Questionnaire-9 (PHQ-9; Appendix VI)[82]: A valid diagnostic and severity measure for depression, with scores ≥ 10 indicating moderately severe depression. The PHQ9 is used to help guide the investigator during the study enrollment process and to help the investigator monitor the patient with respect to depression after randomization. The study investigator will determine if the person is still eligible for study enrollment. This will take approximately 2 minutes to complete.

11.1.6 Linear Analogue Self-Assessment (LASA; Appendix VII)[83]: Single-item LASA items have become the most widely-used assessment in all NCI-sponsored cancer control studies.[84] Normative data have been obtained from various clinical populations enrolled in NCCTG clinical trials and from healthy participants.[85, 86] This will take approximately 3 minutes to complete.

11.1.7 “Was it Worth It?” Survey (Appendix VIII)[87]: This is an end-of-study survey to ask the patient if the entire experience was worth it for them. This will take approximately 2 minutes to complete.

11.1.8 Drug and Behavioral Support Adherence Logs (Appendix X): Each patient will be provided with an adherence log which is specific to his/her treatment phase. In this log, they will provide details of their daily pharmacotherapy intake, contacts made to/from the telephone quitline, amount of cigarettes smoked (if any), and any other comments the patient feels is pertinent. This will take approximately 5 minutes to complete.

11.2 Biochemical confirmation using salivary cotinine

Biochemical confirmation will be used in the cotinine analysis in saliva. Cotinine analyses are two of five validated methods to analyze and verify smoking in patients during smoking cessation.[93-95] Salivary cotinine will be analyzed using the commercially available quantitative enzyme linked immunosorbent assay (ELISA),[96] which we have used in several prior studies.[97, 98] Using salivary cotinine will allow for testing of clinically useful measures. All saliva will be shipped to the Medical University of South Carolina, Charleston, SC per Section 6.2.2. The correlative analyses will be performed in the laboratory of [name] at MUSC.

11.3 Definitions of analysis variables

Formal definitions of variables used in analyses can be found in the Statistical Considerations section of the protocol.

12.0 END OF TREATMENT/INTERVENTION

12.1 Duration of Treatment

Patients should be treated with varenicline/placebo for 12 weeks.

If the patient discontinues varenicline/placebo before completing 12 weeks of therapy, patients should be followed for the duration of the study period (6 months).

12.2 Definitions and Follow-up Requirements

Definition of ineligible patients: A study participant who is registered to the trial but does not meet all of the eligibility criteria is deemed to be ineligible. Patients who are deemed ineligible may continue protocol treatment, provided the treating physician, study chair, and executive officer agree there are no safety concerns if the patient were to continue protocol treatment. Notification of the local IRB may be necessary per local IRB policies.

Definition of clinical follow-up: The follow-up period where the study participant is no longer receiving treatment, but is still following the study calendar for tests, exams, and correlative endpoints (e.g., specimen collection, quality of life, disease assessments as required by the study).

Baseline data must be submitted per Section 5.0 for patients deemed ineligible or canceled. See also the Forms Packet for full details of data submission requirements

12.2.1 Follow-up for Ineligible Patients

Study participants who are registered to the trial but deemed ineligible must complete follow-up requirements.

Baseline, on-study, endpoint (e.g., relapse or progression), off treatment, and survival data submission required.

12.2.2 Follow-up for Patients Never Receiving Protocol Intervention

Study participants who receive the study intervention (varenicline/placebo and behavioral module), but never go on to have the surgery, can complete study intervention if they wish. Data on outcome and complications (adverse events) will continue to be collected, but these patients will not be included in the analysis of the primary endpoint.

Study participants initiate the study intervention (varenicline/placebo and behavioral module), go on to receive surgery, but wish to stop study intervention thereafter, will continue to have data on outcome and complications (adverse events) collected. These data will be used in the analysis of the primary endpoint.

Study participants who were registered/randomized but never received varenicline/placebo will be considered “canceled” and baseline data must be submitted per Section 5.0..

12.3 Extraordinary Medical Circumstances

If, at any time the constraints of this protocol are detrimental to the patient's health and/or the patient no longer wishes to continue protocol therapy, protocol therapy shall be discontinued. In this event:

- Document the reason(s) for discontinuation of therapy on data forms.
- Follow the patient for protocol endpoints as required by the Study Calendar.

13.0 STATISTICAL CONSIDERATIONS

13.1 Study Design

This is a randomized, double-blind, placebo-controlled, phase III trial evaluating varenicline vs. placebo for reduction in post-surgical complications through 24 weeks after surgery in lung cancer patients who undergo surgery and are motivated to stop smoking. A parallel group design will be utilized for this two-arm study: varenicline vs. placebo. Both arms will also include a brief no smoking message from the surgical team and the NCI Quitline.

13.1.1 Study Populations

Intent-to-Treat (ITT) Population: Consists of all randomized patients who had surgery. The ITT population will be used for the efficacy evaluation at each of the planned analyses. Following the intent-to-treat principle, patients will be analyzed according to the treatment they were assigned at randomization. Patient with missing values will be considered to have complications.

Safety Population: Consists of all patients who were randomized, had surgery, and who have at least one post-baseline safety assessment. The safety population will be used in the safety data summaries. Note that a patient who had no adverse events (on the Adverse Event CRF) constitutes a safety assessment. Patients who have received at least one dose of study drug but have no post-treatment safety data of any kind would be excluded.

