1.1.3 Potential for Smoking Cessation Opportunities in Surgical Cancer Patients

Women smokers are 25.7 times more likely than women who never smoked to develop lung cancer. For men smokers, it's 25 times the risk of men who never smoked.[25] Among cancer patients who smoke, 85%-87% of cancer patients want to stop smoking.[26, 27] In one clinical trial, of the 263 cancer participants, the retention rate was approximately 84.5%.

Teachable Moment: Smokers with cancer presenting to a surgeon present a unique opportunity to intervene on smoking behavior. Opportunities in which patients have enhanced susceptibility to interventions on unhealthy behaviors are referred to as “teachable moments.” Use of teachable moments can occur at office visits (associated with 2–10% success in smoking abstinence), notification of abnormal test results (7–21% success), pregnancy (10–60% success), and hospitalization and disease diagnosis (15–78% success).[28] Available evidence suggests that major surgery for a smoking-related cancer provides a significant and effective teachable moment for smoking cessation. A study of 5498 individuals demonstrated that older individuals (≥ 50 years) were more likely to quit smoking after a major medical procedure.[29] The steps in using a teachable moment to help smokers quit smoking include simple physician advice to quit, brief behavioral interventions provided by physicians or other clinicians, and pharmacotherapy.[30, 31] A recent randomized controlled trial testing the clinician-delivered message versus no message has shown randomizing within a site can be successful.[32]

Pharmacotherapy: Varenicline is a partial agonist/antagonist that binds with high affinity and selectivity at the $\alpha 4\beta 2$ neuronal nicotinic acetylcholine receptors. It has been approved by the Food and Drug Administration (FDA) as a stop-smoking aid. Varenicline is presently the most efficacious pharmacotherapy for increasing smoking abstinence rates, with proven superiority over bupropion and suggested superiority over nicotine replacement therapy.[33, 34] In a head to head comparison of varenicline vs. bupropion the odds ratio (OR) at end-

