1.3 Study Overview

This will be a randomized clinical trial. The primary goal is to assess the effect of smoking cessation treatment on surgical complications. We will also report the impact of alternative treatments on QOL and post-operative care. According to the US Guidelines[1], although counseling and medication are effective when used alone, the combination of both is more effective than either alone. Thus clinicians should encourage smokers who want to quit, to use both counseling and medication in trying to quit smoking (#7 of the 10 key guideline recommendations). In this study, 626 cancer surgery patients will be randomized 1:1 to a "protocolized" smoking cessation program (varenicline plus a brief no-smoking message from the surgical team and behavioral support provided by a telephone smoking quitline [NCI's [name]]), or to placebo plus a brief no-smoking message from the surgical team and behavioral support provided by the telephone smoking quitline). Surgery must occur after the target quit date (TQD) defined at baseline and can be performed no sooner than 10 days after randomization and no more than twelve weeks after randomization. The study will remain open to accrual until 626 patients have had surgery and are followed for 24 weeks after surgery for surgical complications. The primary outcome will be the rate of surgical complications, as identified from an investigation of the American College of Surgeons-National Surgical Quality Improvement Program (ACS-NSQIP). Secondary outcomes include QOL, post-operative care (length of hospital and high dependency unit stay), and rates of smoking abstinence. All study participants will have the option of enrolling in the correlative genetic study. This correlative study will look at important genetic variants in nicotinic receptor gene cluster (*CHRNA5-CHRNA3-CHRNA4*) and nicotine metabolism (*CYP2A6*) that have been shown to impact successful smoking abstinence. This will include a blood draw at baseline, and tobacco use outcome will be determined by salivary cotinine at baseline and every six weeks after surgery for 12 weeks, with a final measurement at 24 weeks.

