13.4 Additional Analyses

We will compare changes from baseline in patient quality of life related domains (LASA-12, PHQ-9, SEQ12) between the intervention and control groups using analysis of covariance and linear mixed model repeated measures analysis for each assessment domain. Specifically, we will analyze each LASA domain with a separate ANCOVA model using the change from baseline to 12 weeks post-surgery as the dependent variable, followed by a similar analysis using the change from baseline to 24 weeks post-surgery. Each LASA question corresponds to a separate domain. For the PHQ-9 and SEQ12, we will use the scale scores in a repeated measures analysis involving data from all time points (baseline, 6, 12, and 24 weeks). For the PHQ-9 there is one overall score and for the SEQ12 there are two scales (internal stimuli and external stimuli).

The WIWI survey will be analyzed by comparing the proportion of patients at the end of the treatment period (i.e., 12 weeks after surgery) and at 24 weeks after surgery who endorse each treatment (intervention versus control) via Fisher's exact testing.

These QOL-related domain variables will be included in the modeling process of the primary and other secondary analyses as potentially concomitant confounding covariates so as to produce more efficient estimates from the models. Sensitivity analysis for potential differences between groups demonstrated via the ANCOVA and repeated measures models will be assessed using Generalized Estimating Equations models to account for the correlation of repeated measures on the same patient.

We will compare post-operative care (length of hospital and high dependency unit stay) between the intervention vs. control groups using separate logrank testing of Kaplan-Meier estimates for length of hospital stay and length of high dependency unit stay and supplemented by Cox models to control for concomitant covariates. The assumptions underlying the Cox model will be tested for veracity.

For the expanded complication rate, we will utilize the same analysis approach as the primary endpoint analysis for all complications listed in Appendix I. We will also compare the incidence rates of each specific type of complication between arms.

We will also measure treatment adherence. The number of study visits completed by each patient during the treatment phase will be summarized and compared between groups using the rank

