13.6 Power/Sample Size

The primary statistical endpoint for this study is the incidence of surgical complications as described in Sections 13.1 and 13.3. Patients that have any of these individual morbidities will be considered to have a perioperative complication. Patients without any of these individual morbidities will be considered to not have a perioperative complication.

In a study of 635,265 non-cardiac surgical cases treated in 200 centers throughout the United States, the incidence rate of the perioperative complications listed above from the National Surgical Quality Improvement Program (NSQIP) data was in the range of 25–30%. They further found that smokers undergoing non-cardiac surgery had an estimated 40% increased odds of developing major morbidity and mortality within 30 days of surgery over never smokers, representing a modest difference of between 10%-12% in the actual percentage of patients with major morbidity.[90] One report focused on the limitations of NSQIP in identifying adverse events following major cancer surgery. NSQIP does not abstract the complications considered most important by many surgical subspecialists (e.g., anastomotic leak).[91] Therefore, the true impact of smoking on adverse surgical events may be greater in this trial.

For the purposes of this power calculation then, we will assume a 30% perioperative complication incidence rate in the control group.¹⁰⁴ The study design is a randomized clinical trial intended to estimate the incidence rate of perioperative complications in patients who are smoking at the time of enrollment. The primary statistical analysis will be a comparison of the perioperative complication incidence rates from the time of surgery to 24 weeks after surgery between the intervention and control groups. We will hence power the study to detect a 10% difference in perioperative complication rates between the intervention and control groups.

With a sample size of 626 patients (313 patients per arm), a Fisher exact test can detect a difference in the perioperative complication rate between the two treatment groups of 10% (20% versus 30% in the intervention arm and control arm, respectively) with 80% power using a Type I error rate of 5% and a two-sided alternative.

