The prevalence of smoking among lung cancer surgical patients is roughly 42%.[91] We estimate that 90% of these patients will be motivated to quit and enroll on the study, given the relaxed eligibility requirements requiring only a desire to quit and teachable moment delivery by the surgeons. Hence we can expect to screen roughly three patients to enroll one. An adjustment is also needed for patients that enter the smoking cessation part of the study, but drop out before surgery. We expect that at most 20% of the patients entering the study will drop out after registering and before having surgery. To obtain a sample size of 626 smoking patients with a new diagnosis of lung cancer for which surgery is indicated, we will need to screen

approximately 1878 oncology patients undergoing surgery to enroll 783 smoking patients. Of these 783 patients, we expect 626 to undergo surgery. The study will remain open to accrual until 783 patients have been enrolled. If we take into consideration patient refusal, we would need to approach 2000 smoking oncology patients undergoing surgery to have 626 patients enroll in the study and undergo surgery.

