13.7 Accrual rate and study duration

From accrual estimates provided by sites in this survey, we anticipate accruing 150 evaluable patients per year. Multiple surveys have been conducted to obtain realistic accrual expectations as well as detailed descriptions as to how patients will be accrued, treated, and assessed at each site. This study accrual will close when 783 study patients have been enrolled; therefore, we anticipate patient accrual to be completed in approximately 4 years and 2 months. If, after 400 patients have been enrolled to the study, the proportion of patients who fail to undergo surgery is $\leq 10\%$; then accrual to the study will be stopped when 700 patients have been enrolled, as this would produce the required 626 patients for the primary analysis.

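### Interim tests of the 24-week endpoint admit patients whose window is still open, and the missing-as-complication rule has neither a power allowance nor a sensitivity analysis

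*Combined protocol and SAP*

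**What the plan says.** **Endpoint and interim.** Section 13.2.1 defines the primary endpoint as any of six listed complications within 24 weeks after surgery, and a patient with none of them counts as having no complication. Section 13.10 plans efficacy looks alongside the semi-annual monitoring board reports, each with a bound of 0.001, on everyone who has been on study for 3 months or more. It does not define when time on study starts, and it does not say how an unfinished 24-week window is scored. Surgery falls between 10 days and 12 weeks after randomization (1.3, 3.2.2).

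**Missing outcomes.** Section 13.1.1 takes all randomized patients who had surgery as the ITT set, uses that set at every planned efficacy analysis, and adds: "Patient with missing values will be considered to have complications".

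**Power.** Section 13.6 compares 20% with 30% by Fisher's exact test in 313 patients per arm, "with 80% power using a Type I error rate of 5% and a two-sided alternative". The 30% comes from an external surgical database. The only attrition allowance is that "at most 20% of the patients entering the study will drop out after registering and before having surgery", and those patients are outside the ITT set.

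**Other analyses.** The one analysis labelled as a sensitivity analysis is for the quality-of-life models: "Sensitivity analysis for potential differences between groups demonstrated via the ANCOVA and repeated measures models" (13.4). That section also compares the number of completed study visits between arms by a rank sum test, and compares each type of complication between arms.

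**The concern.** A patient admitted to an interim look at 3 months cannot yet have a complete 24-week outcome. If that patient is event-free so far, two sections point in opposite directions: 13.1.1 can be read as making the patient a complication, and 13.2.1 as making the patient event-free. Neither is the 24-week outcome. Whoever programs the interim report has to choose, and the choice changes the chance that the bound is crossed.

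At the final analysis the same rule adds complications to both arms alike. That narrows the expected difference and raises both rates. Section 13.6 computes power as if every operated patient had an observed outcome. If missingness differs by arm, the rule also shifts the comparison itself, and no planned analysis shows how far the primary result depends on it.

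**Working it through.** All power figures are exact enumerations of the two-sided Fisher test with equal arms.

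**1. The plan's own figure.** Inputs from 13.6: 20% vs 30%, 313 per arm, two-sided 5%. Exact power is 80.2%. Enrolment is 626/0.80 = 782.5, rounded up to 783. Both agree with the plan, and neither leaves room for missing outcomes after surgery.

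**2. Follow-up at the interim cut-off.** Three months is 91 days. Counted from randomization, time since surgery runs from 91 - 84 = 7 days (1.0 week) to 91 - 10 = 81 days (11.6 weeks). Counted from surgery it is 13 weeks, 11 short of 24.

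**3. Chance of p<=0.001 at month 36, counted from randomization.** Assumptions: uniform accrual of 783 over 50 months (the 4 years 2 months of 13.7), 20% lost before surgery, surgery at day S = 28 or 56, true rates 20% vs 30%.

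- Operated per arm per month: 783 x 0.80 / 2 / 50 = 6.264.
- Admitted per arm: 6.264 x (36 - 3) = 207.
- Closed windows per arm: 6.264 x (36 - (S + 168)/30.44) = 185 or 179.
- Open share s = 10.4% or 13.2%.
- f = share of open-window patients' complications already seen, assumed 0.5 to 1.0.

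| Scoring | Rate used | n per arm | S=28 | S=56 |
|---|---|---|---|---|
| Closed windows only | p | 185 / 179 | 11.6% | 11.0% |
| Open = complication | s + (1-s)p | 207 | 7.4% | 6.2% |
| Open = event-free | p(1 - s(1-f)) | 207 | 12.8-14.6% | 12.3-14.6% |

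Counted from surgery, the open share at month 36 is about 8%, so the convention matters less. At month 12 the chance is about 1% or less under every convention.

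**4. Type I error at interim.** With no true effect, a convention applied alike to both arms creates no difference. Nine looks (months 6 to 54) at 0.001 can add at most 9 x 0.1 = 0.9 points to the final test's 4.1%, so at most 5.0%. Simulation of the nine looks (60,000 trials per setting) gave 4.2-4.4% under every convention.

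**5. Final analysis, missing fraction m.** The documents give no post-surgery missing rate, so m is an assumed range, equal by arm and unrelated to outcome. The scored rate is m + (1-m)p, and the difference becomes 10(1-m) points.

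| m | Scored rates | Power under the rule, 313 per arm | Power if the same patients were omitted |
|---|---|---|---|
| 0% | 20.0 vs 30.0 | 80.2% | 80.2% |
| 1% | 20.8 vs 30.7 | 78.6% | 79.9% |
| 2% | 21.6 vs 31.4 | 77.0% | 79.4% |
| 5% | 24.0 vs 33.5 | 72.2% | 78.0% |
| 10% | 28.0 vs 37.0 | 64.2% | 75.7% |

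**6. If complicated patients are more often missing.** Let an event-free patient be missing with probability a and a complicated one with probability r x a, set so that 0.7a + 0.3ra = 5% in the control arm. The scored rate is p + (1-p)a. For assumed r = 2, 3 and 5, a = 3.85%, 3.13% and 2.27%, and power is 74.1%, 75.2% and 76.6%, against 72.2% at r = 1.

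**7. Unequal missingness, 5% vs 7% (hypothetical), 313 per arm, unrelated to outcome.**

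- No true effect, 30% in both arms: 33.5% vs 34.9% scored. Rejection is 5.5% instead of 4.1%.
- 20% vs 30%, control loses more: 24.0% vs 34.9%. Power is 83.1%.
- 20% vs 30%, varenicline loses more: 25.6% vs 33.5%. Power is 55.0%.

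**The case against.** Several points on the other side stand.

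- **Missingness may be small.** Two components end at day 30. Surgical events are collected at weeks 6, 12, 18 and 24, with telephone contact allowed at weeks 12 and 18. Follow-up continues after drug is stopped, and 13.2.1 says sites were surveyed to ensure that the elements can be recorded. At 1-2% the cost is 2 to 3 points of power.
- **Accrual may supply a cushion.** Section 13.6 says "The study will remain open to accrual until 783 patients have been enrolled". If just over 10% are lost before surgery, that gives about 783 x 0.90 / 2 = 352 per arm, with power 82.0% at 2% missing and 77.5% at 5% on the assumptions of step 5. The cushion is not assured, because 1.3 says "The study will remain open to accrual until 626 patients have had surgery". At 10% loss or less, 13.7 says "accrual to the study will be stopped when 700 patients have been enrolled", which at 10% is 315 per arm and 77.2% at 2% missing.
- **The interim effect is mainly on one reading.** If open windows count as event-free, crossing is close to the closed-window figure. The clear drop needs an outcome not yet due to be read as missing, which 13.1.1 does not say in terms.

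Three stronger readings are tempting but not supported. A reader might take the background remark that "of the 263 cancer participants, the retention rate was approximately 84.5" percent as a forecast of 15.5% missing. It is whole-study retention in another trial, not ascertainment of complications. A reader might say that nothing planned could reveal unequal loss. The visit-count and per-complication comparisons in 13.4 might hint at it, though they would not quantify its effect on the primary result. And a reader might infer that the interim looks inflate type I error; step 4 shows that they do not materially.

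**Conclusion.** The concern holds as a gap in specification, and the interim part leads. As written, 13.10 does not test the 24-week endpoint, and the plan leaves open which of two conventions applies. At month 36 the chance of crossing is 6-7% or 12-15% depending on that choice, against 11-12% with closed windows. These figures rest on the assumed accrual, surgery timing and clock of step 3.

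For the final analysis, it would be wrong to conclude that the sample size is miscalculated or that the trial is shown to be underpowered. The 80% is correct for its stated inputs. What is missing is a statement that it presumes complete outcomes after surgery, and any sensitivity analysis of the primary outcome to the missing-data rule. The loss to 77.0% at 2% and 72.2% at 5% depends on missingness that is equal by arm and unrelated to outcome. It is smaller (74.1-76.6% at 5%) if complicated patients are more often missing. A 2-point imbalance between arms matters more for power, in either direction, and is the main reason for a sensitivity analysis.

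**What to change.** 1. **13.10:** restrict each interim efficacy test to patients whose 24-week post-surgery window has closed, including the 14-day visit allowance in the study calendar. State that an outcome not yet due is not missing. Cost: fewer patients at each look. At month 36 the allowance removes a further 6.264 x 14/30.44 = 2.9 per arm, leaving about 177-182 instead of 207.
2. **13.1.1 and 13.3:** keep missing-as-complication as the primary rule, and pre-specify one sensitivity analysis that does not score patients lost event-free as complications, such as multiple imputation. Its cost is a missing-at-random assumption, which should be stated. A time-to-event incidence is an alternative only if onset dates are recorded and deaths after day 30, which are not endpoint events, are handled as competing events.
3. **13.6, optional:** say that the 80% presumes complete post-surgery outcomes, and label any power quoted under the rule with its assumptions. The restated figure may read below 80%.

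These are wording changes. No extra patients or visits are needed.
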